## 3. Outcomes

### *3.1 Primary outcome*

Patient utility surveys will use a 5-point Likert scale for responses scored 1-5. The two co-primary outcomes will compare the scores for the following two questions, **measured at 6 months (or 3 months if the patient did not complete their 6 month survey)**, between **intervention patients** (Arms B + C) and **control patients** (Arm A).

- How well do you feel your oncology team understands your symptoms (e.g. nausea, vomiting, weight loss, etc.)?
- How well do you feel your oncology team understands your activity level and ability to function?

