## 5. Study design

### 5.1 Design

[figure not shown]
This prospective cohort study will evaluate the effect of remotely collected PROs and step data derived from wearable Fitbit devices, and remotely presenting those data to clinicians and patients at each oncology visit. We will enroll patients who are diagnosed with incurable lung or gastrointestinal cancer who are receiving (or planning to receive) chemotherapy. Eligible patients can have in-person or virtual visits with their oncology clinician prior to chemotherapy, which is of particular importance as many visits are now being done via telemedicine. Patients will be randomized into one of three arms – a control (arm a), an intervention with no patient feedback (arm b), and an intervention with patient feedback (arm c) – at a 1:1:1 allocation (**Figure 1: Patient Arms**). All intervention patients will receive 1) weekly PRO surveys for five symptoms administered through the W2H text platform and 2) a Fitbit wearable device that can track patient step, distance, active minutes, sleep, and heart rate data. At each subsequent medical oncology visit (either in-person or via telemedicine), oncology clinicians will receive a PROStep Dashboard that reports the patient’s 1) trends in the home-based PROs and step data, 2) acute care utilization in the prior six months (Oncology Evaluation Unit, emergency department or inpatient admissions), and 3) whether the patient has a documented Serious Illness Conversation (a type of Advance Care Planning note that is standard practice at PCAM). Arm C will receive a brief text message feedback including an active nudge question on their upcoming appointment.

Arm B will not receive text feedback. Arm A will receive no PRO surveys, Fitbit device, or patient feedback (arm a) (**Figure 2: Intervention by Patient Arm**). Patients will be enrolled for a total of six months, unless they disenroll earlier, and evaluated on the outcomes described above.

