A severe symptom ( $\geq 3$ ), or any abrupt change in symptom severity ( $\geq 2$ ), will trigger an alert to the participant's care team via an EPIC message to the attending clinician's symptom pool inbox, whose clinicians will be empowered to intervene at their discretion. Possible interventions might include a telephone call, prescription medication, home care visit, same-day office visit, urgent care, and/or acute care referral. The CRC will review all text message responses each non-holiday weekday for other responses that may warrant closer attention by clinical teams and will call the primary oncology team or send an EPIC message, as appropriate. The CRC can call the study investigators or primary oncology teams at any time to determine whether a text message requires further action.

Until 30 PRO surveys have been sent (e.g. 10 patients for 3 weeks, or 3 patients for 10 weeks), the study investigators and CRC will have a weekly meeting to review the number of responses that cross the alert threshold hold, any text message responses and identify any changes to the protocol that may be needed to ensure the adequacy of this safety mechanism. After this period, the CRC will discuss any concerning text messages to the study investigators.

Patients may opt out of the text message intervention at any time by responding to a W2H text message with the phrase "Stop". The CRC will contact the patient by the next non-holiday weekday to determine whether the patient would like to 1) resume receiving the text messages (in which case they will be reactivated), 2) continue in the trial without receiving the text messages, or 3) withdraw from the trial.

If a patient in the intervention group does not respond to two weekly surveys the CRC will contact the patient to inquire about obstacles to participation (e.g. mobile phone has changed, patient does not wish to participate, etc). Patients will be provided with the CRC's email and phone number to contact with any questions.

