## **Step monitoring**

At enrollment, the CRC will instruct patients on how to wear the Fitbit device and periodically sync the device with their phone to send step data to W2H, as described above. As the device has a 5 day memory, patients will receive a reminder to sync Fitbit twice per week as well as two days before a clinic visit unless the data was synchronized in the prior 24 hours. If patients have no step data transmitted for a two week period, the CRC will contact the patient. Note that while step data will be collected to assess activity, GPS data will not be collected or used in this study.

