## **Clinician surveys**

At 3 and 6 months after patient enrollment, the patient’s oncology clinician team (the attending oncologist and associated advanced practice providers that had an encounter with the patient during the study period) will receive an emailed survey to assess the clinicians’ perspectives on the utility of the PROStep Dashboard for the specific patient (**Appendix I**). Clinicians will be surveyed for each intervention patient (arms b and c) enrolled in the study including patients who

disenroll early but were enrolled for at least 4 weeks of the enrollment period for the upcoming survey.

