### **Patient surveys**

At 3 and 6 months after enrollment, all patients (arms a, b, and c) will receive a text message with a link to a survey to assess the patients' perspectives (**Appendix J**). Patients are eligible to receive these surveys if they are enrolled in the study for a minimum of 4 weeks.

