## **9. Analysis plan**

For each primary outcome, we will compare the mean scores from the survey questions at 6 months (see section 3.1) for all 3 groups (2 intervention, 1 control) using a Kruskal-Wallis test with  $p < 0.05$  indicating statistical significance. If the result is significant, we will use the Tukey's honestly significantly difference (HSD) test to test pairwise comparisons. If the outcomes for any arm are skewed (not normally distributed), we will use log-transformation before applying all tests. For

clinicians who have completed a 3-month survey for a specific patient, but do not complete a 6-month survey for that patient, we will apply their 3-month survey responses in place of their missing 6-month survey for analysis for that specific patient. For example, if Clinician A completes a 3-month survey for Patient A, but not a 6-month survey, we will use the results from their completed 3-month survey in its place for Patient A (but not for other patients). That said, we will do a sensitivity analysis only using the coded 6 month analyses (complete case analysis).

We will repeat this analysis for the secondary outcome of composite survey score at 3 months. For patients who exit the study early, we will attempt to administer their next survey and use that assessment. These will be administered if patients have been enrolled for a minimum of 4 weeks of the enrollment period leading up to their following survey. For example, if a patient disenrolls 4 weeks after receiving their 3-month utility survey, they will be eligible for their 6-month survey whereas a patient who dis-enrolls at 3 weeks will not). If a patient dies or is otherwise unable to complete a survey, they will be omitted from the analysis for the relevant outcome. For patients who disenroll from the trial for any reason (voluntary, death, etc.), but meet this 4 week threshold, their clinicians will receive a utility survey. To assess whether responses in 3-month to 6-month surveys differ across arms, we will run an analysis of covariance (ANCOVA) model with the baseline score and arms as covariates, and change of score as the dependent variable.

We will use descriptive statistics to compare the secondary outcomes of adherence rates between the two intervention groups and trends in PROstep data. We will use Kruskal-Wallis tests for continuous outcomes and chi-square tests for categorical variables to compare these outcomes between all arms at 3 and 6 months.

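### Patients who disenrol in the first 4 weeks never receive the co-primary surveys, and Sections 8.3 and 9 disagree on who receives the 6-month survey

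*Combined protocol and SAP*

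**What the plan says.** The co-primary outcomes (Section 3.1) are two 5-point patient survey items, compared between Arms B + C and Arm A at 6 months, "or 3 months if the patient did not complete their 6 month survey". Who is sent the survey is set in two places.

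- Section 8.3, Patient surveys, covering all arms and both time points: "Patients are eligible to receive these surveys if they are enrolled in the study for a minimum of 4 weeks".
- Section 9: "For patients who exit the study early, we will attempt to administer their next survey and use that assessment". This applies to patients who have been "enrolled for a minimum of 4 weeks of the enrollment period leading up to their following survey". The worked example counts the 6-month threshold from the 3-month survey: leaving 4 weeks after it qualifies, leaving 3 weeks after it does not.

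The clinician rule in Section 8.3 is also counted per survey period. It covers patients who "disenroll early but were enrolled for at least 4 weeks of the enrollment period for the upcoming survey".

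Section 9 then omits patients who die or cannot complete a survey from the outcome concerned. It writes out the 3-month substitution for clinicians, and plans one sensitivity analysis restricted to 6-month answers.

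The arms differ in early study contact. Section 5.1 states: "Arm A will receive no PRO surveys, Fitbit device, or patient feedback". Section 8.3 (Remote-PROs) adds: "If a patient in the intervention group does not respond to two weekly surveys the CRC will contact the patient to inquire about obstacles". Section 8.3 (Step monitoring) adds: "If patients have no step data transmitted for a two week period, the CRC will contact the patient".

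**The concern.** Whether a patient is surveyed depends on staying enrolled for 4 weeks, which is settled after allocation. Dropping randomised patients on that basis means that the groups compared are no longer those that randomisation formed. If early leaving differs between B + C and A, and leavers would have answered differently, the co-primary comparison is biased, and no planned analysis would reveal it.

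A difference by arm is plausible. Only B and C have weekly tasks and a device. Only there does the coordinator make contact after two unanswered surveys or two weeks without step data, which can happen as early as weeks 2-3. No comparable contact is described for Arm A.

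A second problem is reproducibility. Two eligibility rules for one survey, and a substitution written out only for clinicians, let two analysts use different answers for the same patient.

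**Working it through.** **1. Who is never surveyed.** The two rules, by time of exit (taking 3 months as week 13 and 6 months as week 26):

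| Exit | Section 8.3 | Section 9 |
|---|---|---|
| Before week 4 | neither survey | neither survey |
| Weeks 13 to 17, after the 3-month survey | 6-month survey allowed | 6-month survey not allowed |
| After week 17 | 6-month survey allowed | 6-month survey allowed |

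A patient in the first row has no 3-month answer, so the Section 3.1 fallback has nothing to use. The 6-month complete-case analysis uses a narrower set of patients and omits them too. The documents do not state exactly when randomisation falls relative to consent. Because arm-specific set-up starts at enrolment, I take the first 4 weeks as post-randomisation.

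**2. How many.** The documents give the target of 125 patients (Section 5.4) and 1:1:1 allocation (Section 5.1), so about 42 in A and 83 in B + C. They give no exit rate. I assume a constant exit rate, deaths included, with a proportion p gone by week 26, and take p from 0.2 to 0.5.

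- Before week 4: 1 - (1 - p)^(4/26). At p = 0.2 this is 3.4%, or 4.2 of 125. At p = 0.5 it is 10.1%, or 12.6 of 125.
- Weeks 13 to 17: (1 - p)^(13/26) - (1 - p)^(17/26). At p = 0.2 this is 0.894 - 0.864 = 0.030, or 3.8 of 125. At p = 0.5 it is 0.707 - 0.636 = 0.072, or 8.9 of 125.

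**3. What unequal early loss could do.** If unsurveyed patients would have scored d points lower, the shift in (B + C minus A) is (loss in B + C minus loss in A) x d. At equal loss the shift is zero. As a deliberately unequal case, take 10% against 3% and d = 0.5 to 1.0:

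- Shift = 0.07 x 0.5 to 0.07 x 1.0 = 0.035 to 0.07 points.
- Surveyed: 42 x 0.97 = 40.7 and 83 x 0.90 = 74.7. With an assumed SD of 1 point, SE = sqrt(1/40.7 + 1/74.7) = 0.195.
- Shift/SE = 0.18 to 0.36. For a simple two-group comparison at two-sided 5%, the false-positive rate becomes about 5.4% to 6.5%.

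On the constant-rate model (26/4 = 6.5 such periods), that pair implies 1 - 0.90^6.5 = 50% of B + C and 1 - 0.97^6.5 = 18% of A gone by 6 months. With such a gap, losses after week 4 would matter more than the 4-week rule. The sign reverses if A loses more or if leavers would score higher.

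**The case against.** The threshold is pre-specified, worded identically for all arms, and secures some exposure before patients judge how well their team understands them. The study calls itself a feasibility study. These points are fair, but a common rule does not ensure equal exclusion when the arms differ in what could cause early exit.

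A reader might infer that B or C patients who stop engaging are recorded as withdrawn before week 4 while similar Arm A patients are kept. The documents do not support this. Contact after missed surveys is to ask about obstacles, and could as easily keep someone in. A patient who texts to stop may resume, stay in the trial without texts, or withdraw. Ceasing to use the tools is therefore not disenrolment, and such a patient can still be surveyed. Arm A patients can also withdraw, and being sent a survey is not the same as answering it. Differential loss is possible, no more.

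A reader might also extend the conflict over the 6-month survey back to week 4, taking Section 8.3 to entitle every 4-week patient to both surveys. But Section 8.3 states a minimum condition and Section 9 the specific rule for early leavers. Only exits in the 4 weeks after the 3-month survey conflict clearly, through Section 9's own example.

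Finally, the omission sentence in Section 9 might be read as dropping patients who answered at 3 months and then died or left. Section 9 refers to Section 3.1, where the patient fallback is explicit, so this reading is unlikely. The wording still needs tidying, because the substitution is spelled out for clinicians only.

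**Conclusion.** The concern holds in a limited form. Patients who disenrol before week 4 are randomised but cannot contribute to either co-primary outcome, and nothing planned recovers them or shows their distribution by arm. On the assumed exit rates they number about 4-13 of 125. That count includes deaths and people who would refuse a survey, so fewer could be recovered. Size and direction of any bias cannot be determined from the documents. Even with markedly unequal early loss, the illustration gives a modest effect, and all its rates, score deficits and SD are assumptions.

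The conflict over the 6-month survey is definite but narrow, about 4-9 of 125 on the same model. It mostly decides which answer is used, because Section 3.1 keeps anyone with a 3-month answer; it decides inclusion only for those without one. The change is worth making because it is cheap and keeps the analysis closer to the randomised groups.

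**What to change.** - Remove the 4-week condition for patient surveys from Sections 8.3 and 9. Send both surveys on schedule to every randomised patient who is alive and has not refused surveys, after checking that the consent covers contact after disenrolment. The clinician threshold can stay if labelled clinician-only, since those results are descriptive.
- State in Section 9 that the patient co-primary outcomes use the 6-month answer, otherwise the 3-month answer, including for patients who die or disenrol after answering at 3 months. State that the 6-month-only sensitivity analysis applies to these outcomes.
- Report non-response by arm, timing (before or after week 4) and reason, with deaths separate.
- If the threshold is kept, use one rule in both sections and report exclusions by arm.

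The cost is protocol and SAP wording, the consent check, the existing text link, and small payments. Section 7 pays $25 per survey, so early leavers cost at most 13 x $50 = $650, plus $25 for each later leaver who now also answers at 6 months. The downside is that some answers will come after little exposure; early deaths and refusals will stay missing.

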## **11. Human research protection**

### *11.1 Data confidentiality*

Computer-based files will only be made available to personnel involved in the study through the use of access privileges and passwords. Wherever feasible, identifiers will be removed from study-related information. Precautions are already in place to ensure the data are secure by using passwords and HIPAA-compliant encryption.

Computer-based records will be stored on the Way to Health (W2H) study portal, supported by the Penn Medicine Academic Computing Services (PMACS) infrastructure, and will only be made available to personnel involved in the study through the use of access privileges and passwords. Wherever feasible, identifiers will be removed from study-related information. Precautions are in place to ensure the data are secure, including use of passwords and encryption, because the research involves web-based surveys.

The W2H Team supports all research studies run on the platform. Default views within the platform for all W2H staff display de-identified participant data. As a part of support and troubleshooting, the W2H team is trained to use only these de-identified views. In rare cases where the issue involves viewing identifiable participant data, the W2H team may need to view this data to assist the study team. The W2H Team are employees of the University of Pennsylvania and Penn Medicine. All W2H team members have completed HIPAA Security training and CITI Protection of Human Subjects Research Training - ORA.

### *11.2 Subject confidentiality*

Research material will be obtained from participant surveys, Fitbit device data and targeted review of the electronic medical record. All participants will provide informed consent for access to these materials. The data to be collected include demographic data (e.g., age, sex, self-identified race, education level), patient baseline characteristics (e.g., comorbidities, performance status), disease-related data (e.g., tumor stage, histology), treatment-related data (e.g., line/type of therapy), process data (e.g. patient adherence to the intervention), and outcome data (e.g. health-related quality of life, symptom burden, step data, acute care utilization). PRO and step

data will be presented to the patient's oncology clinician as described above. The remaining data that is obtained will be used for research purposes only. The same procedure used for the analysis of automated data sources to ensure protection of patient information will be used for the survey data and chart-abstracted data, in that patient identifiers will be used only for linkage purposes or to contact patients. The study identification number, and no other identifying information, will be used on all data collection instruments. All study staff will be reminded to appreciate the confidential nature of the data collected and contained in these databases.

The Penn Medicine Academic Computing Services (PMACS) will be the hub for the hardware and database infrastructure that will support the project and is where the W2H web portal is based. The PMACS is a joint effort of the University of Pennsylvania's Abramson Cancer Center, the Cardiovascular Institute, the Department of Pathology, and the Leonard Davis Institute. The PMACS provides a secure computing environment for a large volume of highly sensitive data, including clinical, genetic, socioeconomic, and financial information. Among the IT projects currently managed by PMACS are: (1) the capture and organization of complex, longitudinal clinical data via web and clinical applications portals from cancer patients enrolled in clinical trials; (2) the integration of genetic array databases and clinical data obtained from patients with cardiovascular disease; (3) computational biology and cytometry database management and analyses; (4) economic and health policy research using Medicare claims from over 40 million Medicare beneficiaries. PMACS requires all users of data or applications on PMACS servers to complete a PMACS-hosted cybersecurity awareness course annually, which stresses federal data security policies under data use agreements with the university. The curriculum includes Health Insurance Portability and Accountability Act (HIPAA) training and covers secure data transfer, passwords, computer security habits and knowledge of what constitutes misuse or inappropriate use of the server. We will implement multiple, redundant protective measures to guarantee the privacy and security of the participant data. All investigators and research staff with direct access to the identifiable data will be required to undergo annual responsible conduct of research, cybersecurity, and HIPAA certification in accordance with University of Pennsylvania regulations.

All data for this project will be stored on the secure/firewalled servers of the PMACS Data Center, in data files that will be protected by multiple password layers. These data servers are maintained in a guarded facility behind several locked doors, with very limited physical access rights. They are also cyber-protected by extensive firewalls and multiple layers of communication encryption. Electronic access rights are carefully controlled by University of Pennsylvania system managers. We believe this multi-layer system of data security, identical to the system protecting the University of Pennsylvania Health Systems medical records, greatly minimizes the risk of loss of privacy. In addition, risk of loss of confidentiality will be minimized by storing completed paper copies of the surveys and signed informed consent forms in locked file cabinets in locked offices accessible only to trained study staff. Each subject will

be assigned a unique identifier without identifying information, and data will be entered into an electronic database using only the unique identifier. Only trained study staff will have access to the code that links the unique identifier to the subject's identity. Electronic data will be stored on secure, password-protected firewalled servers at the University of Pennsylvania.

Data regarding provider performance of Serious Illness Conversations are already shared among providers and will continue to be shared in unblinded fashion as part of the trial. Data regarding acute care utilization in the last 30 days for a provider's deceased patient panel will be shared amongst providers as well. This will occur as part of the intervention but is planned to occur regardless of trial approval as part of quality improvement efforts.

